5.3 MANAGEMENT OF FAILED CELL CULTURES

In the pre-treatment cell culture process, if it is observed that cells cannot be cultured, exhibit abnormal proliferation, or fail to meet quality requirements during quality inspection, it is necessary to investigate the reasons. In such cases, the technical department will design appropriate measures and arrange for the subjects to provide new samples for re-culturing of cells. Cultured cells that do not meet the required standards will be disposed of according to relevant regulations.

If the re-culturing process is successful, the subjects will be included in the clinical trial and proceed as planned. However, if re-culturing fails again, the subject will be excluded from the clinical trial.

6 SAFETY ASSESSMENTS

- Primary Endpoints:

Incidence and severity of cell therapy-related adverse events (AE) within 24 weeks post-treatment.

- Secondary Endpoints:

Incidence of complications during bronchoscopy within 24 weeks post-treatment;

Changes in pulmonary tumor markers compared to baseline at 12- and 24-weeks post-treatment;

Changes in abnormal values of routine safety checks compared to baseline within 24 weeks post-treatment (blood routine, urine routine, blood biochemistry and electrolytes, electrocardiogram).

Frequency and severity of acute IPF exacerbation events within 24 weeks post-treatment.

Corresponding indicators will be tested during follow-up observation, as follows.

6.1 PHYSICAL AND VITAL SIGNS EXAMINATION

Physical and vital signs examination including height, weight, medical history, etc.

6.2 LABORATORY TESTS

- Blood routine: White Blood Cell Count (WBC), Neutrophil Count (Neu), Lymphocyte Count (Lym), Monocyte Count (Mon), Eosinophil Count (Eos), Basophil Count (Bas), Red Blood Cell Count (RBC), Hemoglobin (HGB), Hematocrit (HCT), Mean Corpuscular Volume (MCV), Mean Corpuscular Hemoglobin Concentration (MCHC), Platelet Count (PLT).
- Urine routine: Urine Glucose (U-GLU), Ketones (KET), Urine Bilirubin (BIL), Urinary Urobilinogen (UBG), Urine

Protein (PRO), Urine Blood (BLD), Urine pH, Urine Specific Gravity (SG), Urine Red Blood Cells (URBC), Urine White Blood Cells (UWBC).

- Blood biochemistry: Total Protein (TP), Albumin (ALB), Total Bilirubin (TBIL), Direct Bilirubin (DBIL), Alanine Aminotransferase (ALT), Aspartate Aminotransferase (AST), Alkaline Phosphatase (ALP), Gamma-Glutamyl Transferase (GGT), Lactate Dehydrogenase (LDH), Blood Urea Nitrogen (BUN), Creatinine (Cr), Uric Acid (URIC), Creatine Kinase (CK), Blood Glucose (Glu), Potassium Ion (K⁺), Sodium Ion (Na⁺), Chloride Ion (Cl⁻), Calcium Ion (Ca⁺).

6.3 12-LEAD ELECTROCARDIOGRAM (ECG) EXAMINATION

The 12-lead ECG examination should record heart rate, rhythm, PQ or PR interval, QRS interval, QT interval (uncorrected), and QTc (QT/RR^{1/2}) and give an overall evaluation (normal, clinically insignificant abnormality, clinically significant abnormality, need further explanation). The signed original ECG will be archived at the study center, and the ECG examination result will be recorded on the CRF or eCRF.

6.4 BLOOD GAS ANALYSIS

PH, PaCO₂, PaO₂, HCO₃

6.5 PULMONARY TUMOR MARKERS

The pulmonary tumor markers include the following: Cytokeratin 19 fragment (CYFRA21-1), Neuron-specific enolase (NSE), Squamous cell carcinoma antigen (SCC), Carcinoembryonic antigen (CEA), Carbohydrate Antigen CA125.

6.6 COMPLICATIONS OF BRONCHOSCOPY

Common complications of bronchoscopy include anesthesia accidents, bleeding, pneumothorax, laryngospasm, hypoxemia, infection, post-procedural fever, and other unforeseen events.

6.7 ACUTE IPF EXACERBATION

Acute IPF exacerbation refers to a rapid deterioration of respiratory symptoms, worsening dyspnea, and decline in lung function without any identifiable cause, leading to respiratory failure or even death.

The diagnostic criteria for acute IPF exacerbation are as follows:

- History of IPF, or current clinical, imaging, and/or histological findings consistent with the diagnosis of IPF. If the previous diagnosis was not IPF based on the diagnostic criteria, current imaging and/or lung tissue pathology should indicate usual interstitial pneumonia pattern.
- Exacerbation of dyspnea or worsening of lung function within the past 30 days, not explainable by other causes.
- High-resolution computed tomography (HRCT) of the chest showing bilateral reticular or honeycomb patterns consistent with usual interstitial pneumonia, along with new ground-glass opacities and/or consolidations. If there is no prior contrast-enhanced HRCT, "new pulmonary imaging findings" can be disregarded.
- Absence of evidence for lung infection in tracheal secretions or bronchoalveolar lavage, including routine bacterial, opportunistic pathogen, and common viral examinations.
- Exclusion of other causes, including left heart failure, pulmonary embolism, and acute lung injury caused by other reasons. Causes of acute lung injury may include sepsis, aspiration, trauma, reperfusion pulmonary edema, pulmonary contusion, fat embolism, inhalation injury,

cardiac bypass surgery, drug toxicity, acute pancreatitis, transfusion of blood products, and cell transplantation.

When clinical data is incomplete or does not meet all five diagnostic criteria mentioned above, it is defined as suspected acute IPF exacerbation. Histopathologically, it is typically characterized by the coexistence of usual interstitial pneumonia (UIP) and diffuse alveolar damage (DAD), which may present with organizing pneumonia and significant fibroblast foci. Acute exacerbation leads to a worsening of lung function in IPF subjects, shortened survival time, poor treatment response, and high mortality rate.

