14. 12-lead electrocardiogram: heart rate, PR interval, QRS complex, QT interval (uncorrected), corrected QT interval QTc (QT/RR^{1/2}), and an overall comment (normal, abnormality without clinical significance, abnormality with clinical significance, need more interpretation). The original electrocardiogram with signature will be stored in research center, the results of electrocardiogram examination are recorded on CRF or eCRF.

15. Lung function (ventilation, diffusion): height, weight, forced vital capacity (FVC), forced expiratory volume in 1 second (FEV1), ratio of FEV1 to FVC, diffusing capacity of the lungs for carbon monoxide (DLCO), alveolar ventilation (VA), the ratio of diffusing capacity of the lungs for carbon monoxide to alveolar ventilation (DLCO/VA). DLCO is measured with single-breath method. The examination results within 3 months before cell therapy can be accepted as the lung function test result at the baseline stage.

16. Idiopathic pulmonary fibrosis acute exacerbation: an acute, clinically significant respiratory deterioration without clear cause, acute worsening of dyspnea and decreased lung function, leading to respiratory failure or even death.

17. Patients should be checked again for inclusion at baseline stage. Results of myocardial enzyme spectrum, autoantibody test, lung cancer markers, serological examination for syphilis, HIV, HBV, HCV, and chest HRCT at the screening stage can be accepted.

18. If abnormality with clinical significance was reported when the patient withdraws in advance, the patient should be followed up until the recovery from the adverse events, reaching a stable status or other clear outcomes as required by the investigator

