1.6 CRITERIA FOR DOSE ESCALATION TERMINATION

(1) Adverse events that occurred throughout the study period were assessed and graded according to CTCAE V5.0. Dose escalation should be terminated with one or more adverse events that were the same or similar and believed to be related (possibly, probably or definitely related) to the REGEND001 autologous therapy product reported on two or more patients of the same dose group after autologous transplantation:

1) hematological toxicity related to cell therapy

a) grade 4 neutropenia (ANC) for 3 days or more; or grade 3 and higher neutropenia with fever ($ANC < 1000/mm^3$ with a single measure of oral temperature $> 38.3^\circ C$ or $\geq 38.0^\circ C$ for one hour);

b) grade 3 thrombocytopenia ($25 \times 10^9/L \leq$ platelet counting $< 50 \times 10^9/L$) with overt clinical bleeding symptoms, or grade 4 thrombocytopenia (with or without overt clinical bleeding symptoms);

c) other grade 4 hematological toxicity.

2) non-hematological toxicity related to cell therapy

grade 3 and higher non-hematological toxicity, except:

a) under medical intervention, grade 3 non-hematological toxicity lasting ≤ 72 hours (non-laboratory examination, such as nausea, vomiting, or diarrhea, etc.);

b) under medical intervention, grade 3 or 4 non-hematological toxicity of abnormal in laboratory examination lasting ≤ 7 days (laboratory examination, such as arrhythmia, cardiac insufficiency, and nervous system abnormalities);

c) other toxicity that is higher than baseline level and related to cell therapy, classified as clinically meaningful severe and/or unacceptable toxicity by investigator and sponsor.

(2) Acute IPF exacerbation and severe adverse events that are related (possibly, probably or definitely related) to REGEND001 cell therapy;

(3) Adverse events that making investigator and sponsor believe the dose should not be escalated anymore, regardless of the event grade or reason;

(4) If none toxicity that would terminate dose escalation happened under the highest 3.3 times standard dose, investigator and sponsor will discuss together regarding

whether dose escalation should continue; if discontinued, the study will stop.

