2.2 INCLUSION CRITERIA

- (1) Male or female, aged between 50 to 75;
- (2) Subjects diagnosed with IPF according to guidelines for the diagnosis of idiopathic pulmonary fibrosis 2018 edition;
- (3) Subjects with 30%~79% of the predicted value in diffusing capacity for carbon monoxide (DLCO) and more than 50% of the predicted value in forced vital capacity (FVC) in pulmonary function tests 3 months before screening;
- (4) Subjects with typical High-resolution computed tomography (HR-CT) imaging findings of idiopathic pulmonary fibrosis in the past 12 months;
- (5) Subjects tolerant to bronchofiberscope;
- (6) Subjects fully informed of the purpose, method and possible discomfort of the trial, agreeing to participate in the test, and voluntarily signing the informed consent;
- (7) Subjects with good adherence, willingness to take medication and regular follow-up examinations as required by the protocol ;
- (8) Subjects able to understand and cooperate with the completion of pulmonary function tests.

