7 EFFICACY ASSESSMENTS

- Changes in lung diffusing capacity for single-breath carbon monoxide (DLCO-sb) compared to baseline at 4-, 12-, and 24-weeks post-treatment.
- Changes in Forced Vital Capacity (FVC) compared to baseline at 4-, 12-, and 24-weeks post-treatment.
- Changes in the ratio of diffusing capacity for carbon monoxide/ the alveolar volume (DLCO/VA) compared to baseline at 4-, 12-, and 24-weeks post-treatment.
- Changes in 6-minute-walk test (6MWT) compared to baseline at 4-, 12-, and 24-weeks post-treatment.

Specific procedures are as follows: In the respiratory outpatient department, select a well-lit, well-ventilated, temperature-controlled corridor with a hard, straight, and flat surface, with a distance of 30 meters for the round trip, and place prominent markers at the starting and ending points. Before the test, explain the purpose, methods, and relevant precautions to the subjects. Participants should wear comfortable clothing and shoes during the test and may use walking aids such as canes. Subjects can have a light meal before the test, but should avoid excessive physical activity and warm-up exercises within 2 hours prior to the test. Subjects should sit quietly for at least 10 minutes at the starting point before the test. During the test, the timer should be started, and the subjects should walk at their own pace based on their usual daily activities from the starting point, turn around at the 30-meter endpoint, and the number of cycles completed in each round trip should be recorded. The testing personnel should not walk with the subjects or use overtly suggestive verbal or non-verbal encouragement. If subjects experience fatigue, dizziness, chest pain, intolerable dyspnea, lower limb spasms, cold sweats, or pallor during the test, the test should be immediately stopped. At the end of the test, shout "Stop" and ask the subjects to stop moving, marking their position. Blood pressure and heart rate should be measured before and after the test.

- Changes in the St. George's Respiratory Questionnaire (SGRQ) scale compared to baseline at 4-, 12-, and 24-weeks post-treatment.
- Changes in imaging of lung by high-resolution computed tomography (HR-CT) compared to baseline at 24 weeks post-treatment.

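### The acute-exacerbation definition ties its waiver of new imaging findings to a contrast-enhanced scan the protocol does not request, although every eligible subject has an earlier plain HRCT

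*Protocol*

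**What the plan says.** Sections 6.7 and 15.2.5 of the protocol give the same five diagnostic criteria. The imaging criterion requires bilateral changes consistent with UIP on HRCT, "along with new ground-glass opacities and/or consolidations". The next sentence begins "If there is no prior contrast-enhanced HRCT" and says that in this case the new imaging findings may be left out of account. An event that does not meet all five criteria, or has incomplete data, is classed as suspected.

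Elsewhere the protocol speaks only of HRCT without contrast being mentioned:
- Inclusion criterion (4) in 2.2 requires "typical High-resolution computed tomography (HR-CT) imaging findings of idiopathic pulmonary fibrosis in the past 12 months".
- Note 17 to the flowchart in 1.4 lists the screening results that may serve at baseline, "and chest HRCT at the screening stage can be accepted".
- Section 7, and likewise 8.2, lists "Changes in imaging of lung by high-resolution computed tomography (HR-CT) compared to baseline at 24 weeks post-treatment".

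The frequency and severity of exacerbations within 24 weeks is a secondary endpoint (sections 6 and 8.2). Item (2) of the escalation-termination criteria in 1.6 reads, in part, "Acute IPF exacerbation and severe adverse events that are related" to the cell therapy.

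**The concern.** A waiver of newness makes sense when there is no earlier scan to compare with. Here it depends on a particular type of earlier scan that the trial does not call for, so it is open in cases where a perfectly usable comparison HRCT is on file. Radiological change since treatment is what separates a new acute process from the fibrotic lung the subject had at entry. If newness may be set aside, a finding that predates the cells can help to establish an event attributed to the period after them.

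The waiver is also optional and its reach is unclear. In a multicentre trial (1.1), one centre may use it for every event and another may never use it. The split between confirmed and suspected exacerbations would then partly reflect how centres read one sentence.

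**Working it through.** The plan gives no figure to reproduce, so this is mainly a comparison of passages.

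**1. Which scan triggers the waiver?** A prior contrast-enhanced HRCT. That description appears only in 6.7 and 15.2.5.

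**2. Which scans does the protocol ask for?**

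| Place | Scan | Contrast mentioned? |
|---|---|---|
| 2.2, inclusion (4) | HRCT in the past 12 months | No |
| 1.4, flowchart note 17 | Screening chest HRCT, usable at baseline | No |
| 5.2 | Follow-up CT while cells are being cultured, if needed | No |
| 7 and 8.2 | HRCT at week 24 against baseline | No |
| 1.5 | HRCT in long-term follow-up | No |

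The HRCT row of the flowchart was not legible in the available text, but the flowchart notes do not mention contrast.

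**3. Who has a comparison scan?** Every eligible subject, by inclusion (4). The week-24 change endpoint also presupposes a baseline scan. A waiver limited to subjects with no earlier HRCT would therefore reach no eligible subject. The waiver as worded reaches any subject who did not happen to have a contrast scan outside the trial; how many that is, the protocol does not say.

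**4. What is left of the imaging criterion once the waiver is used?** The text supports two readings.
- *Narrow:* only newness is dropped. Ground-glass opacity or consolidation must be present but may be old. The protocol expects ground-glass in this population, since the HRCT score in section 7 rates its extent.
- *Broad:* the opacity requirement is dropped as a whole. A UIP pattern remains, which inclusion (2) and (4) largely secure at entry.

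On either reading, a finding present before treatment can satisfy the criterion afterwards.

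**5. What still restricts a confirmed event?** Four criteria: an IPF history or consistent findings; worsening of dyspnea or lung function within 30 days without another explanation; negative microbiology; and exclusion of other causes such as heart failure and pulmonary embolism. The second has no numerical threshold, so it does not make good the weakened imaging criterion, but together the four are a substantial filter.

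**6. How much could one event matter?** Groups have 3 to 6 patients (1.3; the fourth has 6). If a report counted confirmed events only, moving one event between categories would change a group's proportion by 1/6 = 17 to 1/3 = 33 percentage points. Item (2) of 1.6 states no minimum number of events of its own. The protocol does not say that only confirmed events count, so this range is conditional.

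**The case against.** The other side has several good points.

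- **The intended meaning can be guessed.** A waiver of newness is naturally read as applying when there is nothing to compare with, and the reference to contrast may be a slip. That is plausible, but it is inference. The sentence stands in two sections, and a centre following it literally would not be deviating from the protocol.
- **The waiver is permissive and partial.** It allows newness to be disregarded and does not require it. On the narrow reading, opacities must still be seen. This stands, and it is why the criterion is loosened rather than void.
- **Consequences are limited.** Item (2) of 1.6 requires relatedness to the cell therapy and also covers related severe adverse events; item (3) lets the investigator and sponsor stop escalation for any event they judge sufficient. Escalation does not hang on this sentence. Section 17.3.2 treats exacerbations descriptively, with no test between groups. Neither 1.6 nor the endpoint is restricted to confirmed events, so a pooled total might not change. All of this stands and lowers the severity. It does not settle how events are classified, because the protocol does not say that the two categories are pooled either.

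A reader might infer more than the text supports. Imaging is not the only objective criterion: microbiology is test-based, other causes must be excluded, and measured lung function can serve for the second criterion. Nor is the waiver shown to apply to every patient, since outside scans are unknown. Nor would a chance dip in lung function make a confirmed exacerbation: 6.7 describes rapid deterioration leading to respiratory failure or death, the worsening must fall within 30 days and be otherwise unexplained, and the remaining criteria must be met too.

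**Conclusion.** The point holds as an inconsistency between the definition and the trial's own imaging. The waiver refers to a scan that no readable part of the protocol requests, while an earlier plain HRCT exists for every eligible subject. Followed literally, it lets pre-existing opacity, or on the broad reading the UIP pattern alone, meet the imaging criterion, and it leaves centres free to classify like events differently.

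The severity is moderate. The rule belongs to the definition of a secondary safety endpoint that is also named in the termination criteria, but four other criteria remain and the analysis is descriptive. No misclassification rate can be derived from the protocol. The conclusion assumes that the illegible flowchart row does not specify contrast and that some subjects have no outside contrast scan.

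**What to change.** Amend the sentence identically in 6.7 and 15.2.5 so that it agrees with the imaging the trial collects:
1. Make the waiver depend on the absence of any prior HRCT for comparison, without reference to contrast.
2. Name the subject's entry or screening HRCT as the scan against which newness is judged when events are classified for the endpoint.
3. State what the waiver removes: proof that the opacities are new, or the opacity requirement altogether.

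This concerns endpoint classification only. It changes no treatment and proposes no change to the termination criteria in 1.6. It would help if the sponsor also stated whether confirmed and suspected events are reported separately.

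The cost is a short text change in two places, with no additional scan or visit. Some events may move from confirmed to suspected, a category that 6.7 already provides, so they would remain visible if both categories are reported.

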11 ADVERSE EVENTS

11.1 DEFINITION OF ADVERSE EVENTS

Adverse Events (AE): Refers to all adverse medical events that occur in subjects after receiving investigational drug. These events can manifest as symptoms, signs, diseases, or abnormal laboratory findings, but may not necessarily have a causal relationship with the investigational drug. They include the following situations:

(1) Exacerbation of pre-existing medical conditions/diseases (including worsening of symptoms, signs, and laboratory abnormalities) that were present before entering the clinical trial.

(2) Newly occurring AEs: Any newly occurring adverse medical condition (including symptoms, signs, and newly diagnosed diseases).

(3) Clinically significant abnormal laboratory values or results that are not caused by accompanying diseases.

Adverse Drug Reactions (ADR): Refers to any harmful or unexpected reactions related to the investigational drug that occur during the clinical trial. There must be at least a reasonable possibility of a causal relationship between the investigational drug and the adverse reactions, which means that the correlation cannot be ruled out.

Significant Adverse Events: Refers to any AE, other than Serious Adverse Events (SAE), that requires specific medical interventions (such as drug discontinuation, dose reduction, and symptomatic treatment), and results in significant hematological or other laboratory abnormalities.

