(4) Hospitalization due to disease progression symptoms and signs during the trial should not be reported as SAEs. However, deaths resulting from disease progression, including its symptoms and signs, should be reported as SAEs.

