15.2.5 ACUTE EXACERBATION OF DISEASE

Acute IPF exacerbation refers to a sudden deterioration of the condition, worsened breathlessness, and decreased lung function without any clear cause, leading to respiratory failure or even death.

The diagnostic criteria for acute IPF exacerbation are as follows:

(1) History of IPF, or current clinical, imaging, and/or histological findings consistent with the diagnosis of IPF. If the previous diagnosis was not IPF based on the diagnostic criteria, current imaging and/or lung tissue pathology should indicate usual interstitial pneumonia pattern.

(2) Exacerbation of dyspnea or worsening of lung function within the past 30 days, not explainable by other causes.

(3) High-resolution computed tomography (HRCT) of the chest showing bilateral reticular or honeycomb patterns consistent with usual interstitial pneumonia, along with new ground-glass opacities and/or consolidations. If there is no prior contrast-enhanced HRCT, "new pulmonary imaging findings" can be disregarded.

(4) Absence of evidence for lung infection in tracheal secretions or bronchoalveolar lavage, including routine bacterial, opportunistic pathogen, and common viral examinations.

(5) Exclusion of other causes, including left heart failure, pulmonary embolism, and acute lung injury caused by other reasons. Causes of acute lung injury may include sepsis, aspiration, trauma, reperfusion pulmonary edema, pulmonary contusion, fat embolism, inhalation injury, cardiac bypass surgery, drug toxicity, acute

pancreatitis, transfusion of blood products, and cell transplantation.

When clinical data is incomplete or does not meet all five diagnostic criteria mentioned above, it is defined as suspected acute IPF exacerbation. Histopathologically, it is typically characterized by the coexistence of usual interstitial pneumonia (UIP) and diffuse alveolar damage (DAD), which may present with organizing pneumonia and significant fibroblast foci. Acute exacerbation leads to a worsening of lung function in IPF subjects, shortened survival time, poor treatment response, and high mortality rate.

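### A respiratory deterioration firmly attributed to the cells cannot be a confirmed acute IPF exacerbation, so it cannot meet the exacerbation limb of stopping rule 1.6(2) or enter the confirmed-exacerbation count

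*Protocol*

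**What the plan says.** - **Definition.** Protocol 6.7 describes acute exacerbation as deterioration with no identifiable cause and sets five criteria. The fifth is "Exclusion of other causes, including left heart failure, pulmonary embolism, and acute lung injury caused by other reasons". The causes of acute lung injury that follow include "cardiac bypass surgery, drug toxicity, acute pancreatitis, transfusion of blood products, and cell transplantation". Section 15.2.5 repeats the criteria and the list, ending with "pancreatitis, transfusion of blood products, and cell transplantation". Note 16 to the study flowchart also requires that there be no clear cause.
- **Cases that miss a criterion.** When data are incomplete or a criterion is not met, "it is defined as suspected acute IPF exacerbation".
- **Escalation stop.** Section 1.6(2) lists "Acute IPF exacerbation and severe adverse events that are related (possibly, probably or definitely related) to REGEND001 cell therapy".
- **Endpoint.** Section 6 lists "Frequency and severity of acute IPF exacerbation events within 24 weeks post-treatment", and section 8.2 has a matching item. Section 17.3.2(5) repeats frequency and severity. None of the three says which diagnostic categories are counted.
- **SAE exception.** Section 12.1(4) states "Hospitalization due to disease progression symptoms and signs during the trial should not be reported as SAEs". Deaths from progression stay reportable.
- **AE definition.** Section 11.1(1) includes "Exacerbation of pre-existing medical conditions/diseases (including worsening of symptoms, signs, and laboratory abnormalities".

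**The concern.** Cells are instilled by bronchoscope into fibrotic lung, so acute respiratory worsening is a harm the trial has to be able to see. The protocol has a dedicated stopping limb and a dedicated secondary endpoint for it. Both rest on a diagnosis that is withheld once the cells are identified as the cause. The stopping limb asks for a link to the cells, and the definition excludes events explained by the cells.

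The SAE rule raises a second, separate question. Whether a hospitalised deterioration is reported as serious depends on whether the investigator calls it disease progression. That judgement is made in one patient at a time, with treatment known and no control group.

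Escalation decisions rest on 3 to 6 patients per dose, so the label given to one event can matter.

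**Working it through.** **Design figures.** Group sizes in section 1.3 are 3–6, 3–6, 3–6 and 6. The minimum is 3+3+3+6 = 15 and the maximum is 6+6+6+6 = 24, which reproduces the planned 15–24. The point itself concerns definitions and does not depend on this total.

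**Step 1: the definition against the stopping limb.** Criterion 5 asks that acute lung injury from another cause be excluded, and cell transplantation is one of the named causes. The exacerbation limb of 1.6(2) asks that the event be at least possibly related to the cells.

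- If the cells are established as the cause, criterion 5 fails and the event is suspected at most. The limb cannot be met unless suspected events count, and the protocol does not say whether they do.
- If no cause is established, all five criteria can hold. Section 11.4 allows a grade of possibly related where disease progression cannot be excluded, so the limb can be met.

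The incompatibility is confined to events firmly attributed to the cells.

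**Step 2: where a deterioration is counted, by label.**

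| Label | Confirmed exacerbation | Exacerbation limb of 1.6(2) | Primary related-AE outcome | SAE if hospitalised, not fatal |
|---|---|---|---|---|
| No cause established, graded possibly related | Yes, if all five criteria hold | Yes | Yes | Yes, unless labelled progression |
| Firmly attributed to the cells | No | Not unless suspected events count | Yes | Yes |
| Criteria incomplete | No, suspected | Not stated | Yes, if at least possibly related | Yes, unless labelled progression |
| Labelled disease progression | Depends on the five criteria | Depends on the criteria and the relatedness grade | Yes, if at least possibly related | No |

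The primary-outcome column follows from 8.1, 11.1(1) and 11.2: worsening of existing disease is an AE, and all AEs are recorded whatever their cause. No row removes a related event from every count.

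**Step 3: what the other limbs of 1.6 recover.** Limb (1) covers related non-haematological toxicity of grade 3 or higher and does not need exacerbation or SAE status. It does require the same kind of event in at least two patients of one dose group, and it exempts some short-lived grade 3 events. The second half of (2) covers related severe events. Limb (3) is open to any event but discretionary. A single cell-attributed deterioration is therefore caught without discretion only if it qualifies as a severe event under (2).

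**Step 4: consequence of the progression label.** Under 13.2 the sponsor's SUSAR evaluation starts from the SAEs it receives. A non-fatal hospitalisation kept out by 12.1(4) does not reach that evaluation.

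**Step 5: size.** One event is 1/6 = 17% of a group of six and 1/3 = 33% of a group of three.

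As an illustration only, assume a true per-patient rate p of escalation-terminating events within the 28-day window. Read section 1.3 as opening the next dose after 0 of 3 events, or after 1 of 3 followed by 0 of 3:

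P(open) = (1−p)³ + 3p(1−p)² × (1−p)³

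For p = 0.30: 0.343 + 0.441 × 0.343 = 0.494. If a fraction of the events is not counted, p is replaced by p × (1 − fraction).

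| Assumed true p | All counted | One quarter not counted | Half not counted |
|---|---|---|---|
| 0.20 | 0.709 | 0.814 | 0.906 |
| 0.30 | 0.494 | 0.654 | 0.814 |

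Neither p nor the uncounted fraction comes from the protocol. The table shows why the label matters. It does not show that events are lost.

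**The case against.** A reader might infer that treatment-caused respiratory harm is defined out of the safety counts altogether, or that the exacerbation trigger can never fire. The documents do not support either reading.

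- The primary outcome takes every cell-related AE over 24 weeks, with no exception for lung injury.
- An event with no established cause can meet the full definition and still be graded possibly related, which satisfies 1.6(2).
- Limbs (1) and (3), and the severe-event half of (2), remain available.
- The two exclusions act on different labels. An event attributed to the cells is not progression, so its hospitalisation is still an SAE.
- Section 12.1(4) does not contradict 11.1(1): an event can be an AE without being an SAE. It stands as a listed exception to the SAE definition. Section 12.2 also treats an event as an SAE while its status is uncertain.
- Limb 1.6(2) speaks of severe events. If that means CTCAE severity, 12.1(4) does not touch it.
- The protocol is silent on suspected events rather than excluding them, and a statistical analysis plan that is not shown may set the tabulation.

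All of this stands, and it narrows the point. It does not remove the mismatch between 1.6(2) and criterion 5 for firmly attributed events. That mismatch sits in a stopping rule, which a tabulation plan would not settle. The default in 12.2 helps only when the investigator is unsure, not when the investigator has decided on progression.

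**Conclusion.** The point holds in a limited form. A deterioration firmly attributed to the cells cannot be a confirmed acute exacerbation, so it cannot meet the exacerbation limb of 1.6(2) and is absent from the confirmed-exacerbation count. Whether it returns as a suspected event is not stated. It stays in the primary related-AE outcome and may stop escalation by another route, although limb (1) needs a second patient in the same group.

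Separately, a non-fatal hospitalised respiratory deterioration labelled progression falls outside SAE reporting and SUSAR assessment. In an open-label trial without a control group, that label is hard to check.

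One event is worth 17 to 33 percentage points of a group's rate. How often an event would be affected cannot be derived from the documents. The conclusion assumes that criterion 5 is applied as written and that an event established as caused by the cells counts as having an identified cause.

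**What to change.** 1. Reconcile 1.6(2) with 6.7 and 15.2.5, and with note 16 to the flowchart, so that the exacerbation limb can be met by the related events it names. State whether suspected exacerbations count for that limb and for the secondary endpoint.
2. Report the secondary endpoint as all acute respiratory deteriorations within 24 weeks, split into definite, suspected, and with identified cause. Show cell transplantation as its own identified cause.
3. Reconcile 12.1(4) with the SAE definition in 12.1 and with the related-event limb of 1.6(2). Say there whether severe means CTCAE severity or seriousness.

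Which clinical rule prevails in items 1 and 3 is for the sponsor to decide.

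The cost is protocol and CRF wording and perhaps a few more reports. The reported exacerbation rate may also look less favourable. No change in sample size or visit schedule is needed.
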